57 primarily to identify modifiable risk factors associated with malnutrition-related morbidity and
58 mortality and assess the effectiveness of targeted nutritional interventions. The secondary objectives
59 include examining variations in nutritional status across cancer types and treatment modalities and
60 exploring how nutritional health interacts with psychological well-being, sleep quality, and physical
61 activity. Participants diagnosed with common malignancies across multiple hospitals undergo
62 baseline nutritional assessments within 48 hours of admission, followed by structured follow-ups at
63 1, 2, 3, 6, and 12 months and then annually for an additional four years to track nutritional changes
64 and key clinical endpoints (Riboli, 2001). Nutritional status, the primary exposure factor, is
65 classified via validated screening tools and dietary intake assessments. Patients are stratified on the
66 basis of malnutrition severity, dietary intake, and nutritional support status, with classifications
67 updated at each follow-up, to evaluate their associations with short- and long-term outcomes (**Fig.**
68 **1**).

[figure not shown]

Fig. 1. The workflow of the NCOM study.

Study Setting & Population

Study sites

The NCOM study was conducted across 11 tertiary hospitals in Xi'an, Shaanxi Province, China.

The participating institutions included Shaanxi Provincial Cancer Hospital; the First Affiliated

Hospital of Xi'an Jiaotong University; the Second Affiliated Hospital of Xi'an Jiaotong University; Shaanxi Provincial People's Hospital; the First Affiliated Hospital of the Fourth Military Medical University; the Second Affiliated Hospital of the Fourth Military Medical University; Shaanxi Provincial Chest Hospital; and the Affiliated Hospital of Northwest University Xi'an No.3 Hospital; Xi'an International Medical Center Hospital; The First Affiliated Hospital of Xi'an Medical University; The Second Affiliated Hospital of Xi'an Medical University.

Recruitment strategy

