Upon enrollment, trained personnel will obtain informed consent and record demographic details, including sex, age, marital status, occupation, education, and socioeconomic status. Lifestyle factors such as smoking, alcohol, and tea consumption are documented, given their potential influence on nutritional status and cancer progression(Yuan *et al*, 2023). Medical history, including chronic conditions, previous diagnoses, medication use, and family history of malignancies, will also be recorded to assess genetic predispositions.

Cancer-specific data will be collected at baseline and updated at follow-ups to monitor disease progression and treatment response. This includes pathology-confirmed diagnosis, TNM staging at first diagnosis, and available molecular markers. The tumor burden will be reassessed at each visit, alongside major treatments (surgery, chemotherapy, radiotherapy, targeted therapy, and immunotherapy), with details on the type, duration, and response. Nutritional support, including enteral or parenteral nutrition in the preceding week, will be tracked to evaluate its impact on treatment outcomes.

Karnofsky Performance Status (KPS): The KPS evaluates a patient's ability to perform daily activities, the presence of physical discomfort, and overall performance status, providing a standardized measure of functional impairment(McNair *et al*, 2023).

Nutritional assessments

Nutritional assessments will be conducted via validated screening tools to evaluate nutritional status, risk factors, and dietary intake patterns. Two primary tools and standardized anthropometric

measurements will be employed to assess malnutrition risk and severity:

Subjective Global Assessment (mPG-SGA): The mPG-SGA scoring system consists of five sections: weight loss history, dietary intake changes, symptoms, activity and function levels, and age. Patients' nutritional status will be categorized on the basis of scores as normal (0–2 points), mild malnutrition (3–6 points), and moderate malnutrition (≥ 7 points)(Huo *et al*, 2023a). The version used in this study, mPG-SGAL11, is an adapted and validated version developed for Chinese cancer patients who that incorporates modifications on the basis of nationwide clinical feedback and statistical validation(Fu *et al*, 2022; Huo *et al*, 2023b).

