Additional biochemical parameters, including hematological markers such as blood glucose, hemoglobin, white blood cell count, neutrophil count, lymphocyte count, red blood cell count, monocyte count, and platelet count, will be recorded where available. The liver and kidney function markers used were AST, ALT, creatinine, blood urea nitrogen, total bilirubin, and direct bilirubin. Lipid profile: Total cholesterol, triglycerides, high-density lipoprotein cholesterol (HDL-C), and low-density lipoprotein cholesterol (LDL-C)(Yang *et al*, 2019).

All values are based on the most recent test results closest to the evaluation. If certain parameters are not routinely available, they will be documented as unavailable. To ensure data reliability, assessments will follow strict quality assurance protocols, including routine calibration of analyzers, standardized sample handling procedures, and interlaboratory validation. When feasible, blood samples will be collected in a fasting state to minimize variability in metabolic markers.

Quality of Life & Psychosocial Factors

A comprehensive assessment of quality of life and emotional well-being will be conducted to evaluate the psychosocial impact of cancer and its treatment on patients. Standardized and validated measurement tools will be used across study sites to ensure the comparability and reliability of the data.

European Organization for Research and Treatment of Cancer Quality of Life Questionnaire (EORTC QLQ-C30): This questionnaire is used to evaluate the overall quality of life of cancer patients. This validated instrument consists of five functional scales (physical, role, cognitive, emotional, and social functions), three symptom scales (fatigue, pain, nausea/vomiting), six single-item symptom measures (dyspnea, appetite loss, sleep disturbance, constipation, diarrhea, and financial difficulties), and a global quality of life scale. Each scale and single-item measure is scored from 0 to 100, with higher scores indicating better quality of life. This tool has been widely applied in oncology research and provides valuable insights into patients' well-being, treatment-related side effects, and overall functionality(Aaronson *et al*, 1993).

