Nutrition support in and out of hospital Nutrition support	√	√	√	√	√	√	√
Laboratory biomarkers	√	√	√	√	√	√	√
EORTC QLQ-C30	√	√	√	√	√	√	√
HADS	√	√	√	√	√	√	√
PSQI	√	√	√	√	√	√	√
Leisure-time physical activity levels	√	√	√	√	√	√	√
KAP Questionnaire	√				√	√	√
Short-Term Clinical Outcome		√	√	√	√	√	√
Long-term clinical outcomes		√	√	√	√	√	√
Adverse Event Recording	√	√	√	√	√	√	√

299 **Table 1.** Follow-up schedule. SV: screening visit; KPS: Karnofsky Performance Status; mPG-SGA:
 300 Subjective Global Assessment; NRS-2002: Nutritional Risk Screening 2002; SDSAT: Simple Diet Self-
 301 Assessment Tool; EORTC QLQ-C30: European Organization for Research and Treatment of Cancer

Quality of Life Questionnaire C30; HADS: Hospital Anxiety and Depression Scale; PSQI: Pittsburgh Sleep Quality Index; KAP : Knowledge, Attitude, and Practice.

Statistical analysis plan

Baseline characteristics are summarized as the means \pm standard deviations (SDs) for normally distributed variables, medians with interquartile ranges (IQRs) for skewed data, and percentages for categorical variables. For group comparisons (e.g., normal vs. mild malnutrition vs. moderate malnutrition patients), independent t tests or Mann–Whitney U tests were used for continuous variables, and chi–square tests or Fisher’s exact tests were used for categorical data.

The primary outcome analysis will apply multivariate regression models, adjusting for age, sex, cancer stage, treatment modality, socioeconomic status, and baseline Karnofsky Performance Status (KPS). Logistic regression was used to assess binary outcomes (e.g., nutritional risk, survival), whereas linear regression was used to evaluate continuous variables (e.g., BMI changes, weight loss percentage). To account for repeated measures, generalized estimating equations (GEEs) model longitudinal variations in nutritional status, biomarkers, and quality of life.

For survival analysis, Kaplan–Meier curves were used to estimate overall survival (OS) and progression-free survival (PFS), with log-rank tests used to compare groups. Cox proportional hazards models were used to explore the associations between nutritional status and survival outcomes, incorporating time-dependent covariates where applicable.

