Secondary analyses will investigate associations between nutritional status and psychosocial factors (e.g., EORTC QLQ-C30, HADS, PSQI) via paired t tests, mixed-effects models, and correlation analyses (Spearman or Pearson, depending on distribution).

To minimize bias and confounding factors, propensity score matching (PSM) will balance baseline differences between exposure groups. Multiple imputation will handle missing data to prevent systematic bias, and sensitivity analyses will exclude cases with extreme values, incomplete follow-ups, or protocol deviations.

Subgroup analyses will stratify findings by cancer type, treatment modality, and nutritional status category. Interaction terms are included in regression models to identify potential effect modifications, with exploratory analyses conducted if unexpected patterns arise.

By integrating multivariate modeling, survival analysis, repeated measures approaches, and

missing data imputation, this study ensures robust, high-quality, evidence-based insights into the impact of nutritional status on clinical outcomes and survival in cancer patients.

Informed Consent Process

Participation in this study is voluntary, and individuals may withdraw at any time without affecting their medical care. Before enrollment, participants and their families will receive detailed study information, including their purpose, methodology, potential risks, and benefits. A written informed consent form must be signed, confirming their understanding and voluntary participation.

The informed consent process will be conducted by trained research personnel, ensuring that participants fully understand the study's objectives and procedures; are aware of their right to withdraw at any time without impacting their current or future medical treatment; and have the opportunity to ask questions and receive clarifications before signing.

To accommodate diverse literacy levels, consent materials will be provided in clear, accessible language, with verbal explanations when needed. The informed consent form included both English and Chinese versions (**Supplementary File 1**).

Data Privacy & Confidentiality

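### When mPG-SGA is the exposure, its symptom and function sections overlap with the QLQ-C30 physical, role and symptom scales, so part of that secondary association is built in

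*Protocol*

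**What the plan says.** **Exposure.** The Study design section says that nutritional status is "classified via validated screening tools and dietary intake assessments" and that the classification is updated at each follow-up. Nutritional assessments names mPG-SGA as one of two primary tools and gives its content: "The mPG-SGA scoring system consists of five sections: weight loss history, dietary intake changes, symptoms, activity and function levels, and age". The total score alone sets the classes: normal (0–2), mild (3–6) and moderate malnutrition (7 or more). The Statistical analysis plan section gives the same three classes as its example of group comparisons: "normal vs. mild malnutrition vs. moderate malnutrition patients".

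**Outcome.** Quality of Life & Psychosocial Factors describes QLQ-C30 as "five functional scales (physical, role, cognitive, emotional, and social functions), three symptom scales (fatigue, pain, nausea/vomiting), six single-item symptom measures", the single items being "dyspnea, appetite loss, sleep disturbance, constipation, diarrhea, and financial difficulties), and a global quality of life scale".

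**Timing.** Table 1 ticks mPG-SGA and QLQ-C30 at the screening visit, at months 1, 2, 3, 6 and 12, and annually thereafter.

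**Analysis.** "Secondary analyses will investigate associations between nutritional status and psychosocial factors (e.g., EORTC QLQ-C30, HADS, PSQI) via paired t tests, mixed-effects models" and Pearson or Spearman correlations. The section also plans GEE models for changes over time in nutritional status and quality of life.

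**The concern.** An exposure score that counts symptoms and function is to be related to an outcome questionnaire that counts symptoms and function, completed at the same visit. A patient with heavy symptoms and poor function but stable weight and normal intake can be placed in a malnutrition class and also score badly on QLQ-C30. An association found this way mixes two things: how nutrition relates to quality of life, and how symptom burden reported on one form relates to symptom burden reported on another.

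The protocol says its results should inform personalised nutritional treatment. For that purpose the two need to be told apart, because an association carried by symptoms says little about weight loss or intake.

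**Working it through.** The protocol gives no figure for the nutrition–QLQ-C30 association, so there is nothing to reproduce. The check compares content first, then illustrates size.

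**1. Content side by side**

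| mPG-SGA section | QLQ-C30 content in the same domain |
|---|---|
| Weight loss history | none |
| Dietary intake changes | none scored as intake; the appetite-loss item is close |
| Symptoms | fatigue, pain and nausea/vomiting scales; symptom single items |
| Activity and function | physical and role function |
| Age | none |

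Two of the five sections share a domain with QLQ-C30. The emotional, cognitive and social scales and the financial item have no counterpart on their face. The comparison works only at the level of domains, because the protocol lists neither the mPG-SGA symptom items nor the section weights.

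**2. Does anything in the plan separate the shared part?** The protocol states no score without the two sections, no restriction to unshared scales and no exposure from an earlier visit. Adjustment for KPS uses the baseline value only and is stated for the primary outcome analysis. It cannot remove shared change at later visits, and simple correlations are unadjusted.

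**3. Illustration of size (all inputs assumed).** Let s be the share of mPG-SGA variance from symptoms and function, q the share of the QLQ-C30 scale's variance from the same domains, and ρ the correlation between those two parts. Set all other parts independent, so that nutrition proper has no relation to the scale. Ignoring sign, r = ρ × √(s × q).

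- s = 0.1, q = 0.25, ρ = 0.5: 0.5 × √0.025 = 0.08
- s = 0.2, q = 0.5, ρ = 0.5: 0.5 × √0.10 = 0.16
- s = 0.3, q = 0.5, ρ = 0.7: 0.7 × √0.15 = 0.27
- s = 0.5, q = 1, ρ = 0.7: 0.7 × √0.50 = 0.495

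Simulation with 200,000 subjects gave 0.082, 0.161, 0.268 and 0.497. Over the full grid (s 0.1–0.5, q 0.25–1.0, ρ 0.3–0.9), r runs from 0.05 to 0.64.

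A heavier set of assumptions (q = 1, s 0.3–0.7, ρ 0.4–0.8) gives 0.4 × √0.3 = 0.22 to 0.8 × √0.7 = 0.67, with 0.6 × √0.5 = 0.42 in the middle. Together the two sets span about 0.05 to 0.67. With s = 0, which is what removing the two sections does, this component is 0.

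**4. Would it be seen?** The smallest r detectable with 80% power at two-sided 0.05 is tanh((1.960 + 0.842)/√(n − 3)).

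- n = 1,538 (the target): tanh(2.802/√1,535) = 0.071
- n = 769 (1,538 × 0.5, the upper end of the protocol's attrition range): tanh(2.802/√766) = 0.101

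Most of the grid lies above both values; its low end of 0.05 lies below both.

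**The case against.** **The exposure is not fixed as mPG-SGA.** The secondary analysis says only nutritional status, and the protocol also collects NRS-2002 (disease severity, nutritional status, age), anthropometry, dietary intake and biomarkers. A separate statistical analysis plan may say which measure enters which model. This stands as a limit: the point applies when mPG-SGA is the exposure. It does not remove the point, because mPG-SGA is a primary tool, its classes are the ones named for group comparisons, and nothing steers the QLQ-C30 analysis to the other measures.

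**Shared items are not shown.** This stands. A reader might infer that both forms ask about the same symptoms, or that the instrument is being correlated with itself. The protocol supports neither reading: these are two instruments, and only overlap of domains is documented.

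**The reach is narrow.** This also stands. The stated secondary objective concerns psychological well-being, sleep and physical activity. HADS is described as omitting somatic items, and three of the five QLQ-C30 functional scales do not overlap on their face.

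**The plan speaks of associations, and the tool is described as validated.** True, and symptoms may belong in a tool for detecting malnutrition. That does not make the total score suitable for separating nutrition from symptom burden when the outcome is symptom burden.

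**Changing the score has costs.** Dropping sections gives up the published cut-offs, and visits are one month to one year apart, which complicates lagged models. These are reasons to keep the total score and add to it, not to replace it.

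**Conclusion.** The concern holds in a limited form. With mPG-SGA as exposure, the planned association with the QLQ-C30 physical, role and symptom scales is partly built in by shared domains measured at the same visit, and the protocol does nothing to separate them.

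The size is unknown. The range of about 0.05 to 0.67 rests wholly on assumed variance shares and correlations, and on setting every other relation to zero. A reader might infer that a spurious significant result is certain. Under the heavier assumptions r = 0.22 at n = 769 would indeed give z = atanh(0.22) × √766 ≈ 6.2, but the low end of the wider grid would not be reliably detected, so certainty is not supported. Nor do the documents show that the study will report an effect of malnutrition on quality of life where none exists; they show that the planned analysis could not tell the two apart.

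The point concerns a secondary analysis and leaves the survival analyses and the sample size untouched. It is a cheap improvement.

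**What to change.** In the Statistical analysis plan section, at the secondary analyses, state that for the QLQ-C30 physical, role and symptom scales the association will be estimated with measures already collected that have no symptom or function section: percentage weight loss, BMI, mid-arm circumference, triceps skinfold, or the mPG-SGA weight-loss and intake sections. Report these beside the total mPG-SGA result, and interpret that result with the overlap stated. For the appetite-loss item the anthropometric measures are the cleaner choice, since the intake section is close to it in content.

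Optionally, add a sensitivity model relating nutrition at one visit to QLQ-C30 at the next, adjusted for QLQ-C30 at the earlier visit and allowing for the unequal intervals.

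No new data are needed. The cost is a little more analysis, a probably smaller association, and less direct comparability with reports that use the total score.

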Nutritional risk screening (NRS-2002): The NRS-2002 screening tool evaluates nutritional risk on the basis of three components: disease severity, nutritional status, and age. A total score of ≥ 3 indicates nutritional risk, warranting nutritional intervention, whereas a score of <3 requires weekly reassessment to monitor changes in nutritional status(Zhang *et al*, 2021).

Standardized anthropometric measurements: These measurements will include body mass index (BMI), percentage of weight loss, mid-arm circumference (MAC), triceps skinfold thickness (TSF), and handgrip strength. All measurements will be made under controlled conditions and repeated to ensure accuracy and reliability. To ensure methodological consistency, all measurements will be taken under fasting conditions, with patients wearing minimal clothing and no shoes.

Simple Diet Self-Assessment Tool (SDSAT): A validated self-reported dietary intake tool will be used to estimate the dietary intake of cancer patients. Compared with 24-hour dietary recall, the SDSAT has good reliability and validity(Jin *et al*, 2020).

Nutrition support in and out of the hospital: To evaluate the nutritional support of patients in and out of the hospital, patients need to provide information on the type of nutritional support (enteral or parenteral), formula, and supplemental dose.

Laboratory biomarkers

Biochemical markers will be analyzed to assess nutritional status, systemic inflammation, and metabolic function. Blood samples will be collected, processed, and stored following standardized protocols to ensure consistency among sites.

Serum ALB, prealbumin, and transferrin can be measured as indicators of protein-energy malnutrition, providing insights into nutritional depletion and muscle wasting risk. These factors

will be analyzed alongside C-reactive protein (CRP) to account for inflammation-related reductions in protein levels[30]. Inflammatory cytokines, including interleukin-6 (IL-6), interleukin-1 (IL-1), and tumor necrosis factor-alpha (TNF- α), serve as markers of systemic inflammation and metabolic dysregulation in patients with cancer-related malnutrition and cachexia(Keller, 2019).

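### The mPG-SGA band of 7 points or more has no upper limit and no class above it, yet it is labelled moderate malnutrition in an exposure meant to be graded by severity

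*Protocol*

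**What the plan says.** In the Protocol, the Study design section begins its exposure definition with "Nutritional status, the primary exposure factor, is" and bases the classification on screening tools and dietary intake. Patients are then stratified on the "basis of malnutrition severity, dietary intake, and nutritional support status, with classifications" refreshed at every follow-up.

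The Nutritional assessments section names two primary tools plus anthropometry. It says that these "measurements will be employed to assess malnutrition risk and severity". For the mPG-SGA the classes are "normal (0–2 points), mild malnutrition (3–6 points), and moderate malnutrition (≥ 7 points". For the NRS-2002 there is one threshold: "A total score of ≥ 3 indicates nutritional risk, warranting nutritional intervention".

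The Statistical analysis plan section gives, as its example of a group comparison, "normal vs. mild malnutrition vs. moderate malnutrition patients". Later it adds: "Subgroup analyses will stratify findings by cancer type, treatment modality, and nutritional status category". Table 1 schedules the mPG-SGA at screening and at every follow-up.

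**The concern.** A severity scale whose worst grade is called moderate, and whose worst grade has no ceiling, does not describe its upper end. Read literally, a patient at 7 points and a patient far above 7 have the same exposure level and the same label.

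Two things are at stake. The first is interpretation: a published association for moderate malnutrition would be read as applying to moderate cases, while the group behind it is everyone at 7 points or more. The second is the longitudinal aim. The Introduction justifies the cohort by the need to capture dynamic change in nutrition, and the class is to be updated at each visit. Within the top band an updated class cannot register improvement or deterioration.

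**Working it through.** The protocol states no figure that rests on these bands. The sample size section speaks only of event rates in an exposed and an unexposed group, so its target of about 1,538 does not depend on them. The check is to apply the stated rule and compare the sections.

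**1. The rule.** Coded as written: score ≤ 2 is normal, 3 to 6 is mild, ≥ 7 is moderate. The higher scores below are illustrative, because the protocol does not give the maximum of the scale.

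| Score | Class |
|---|---|
| 0, 2 | normal |
| 3, 6 | mild |
| 7, 8, 10, 11, 15, 20, 25 | moderate |

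For whole-number scores the bands cover everything from 0 upward without gap or overlap. The normal band holds 3 scores (0 to 2), the mild band holds 4 (3 to 6), and the top band is unbounded. The fault is confined to that top band and its label.

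**2. Change over time under the rule.** A move from 6 to 7 is 7 − 6 = 1 point and changes the class. A move from 20 to 8 is 20 − 8 = 12 points and leaves the class at moderate.

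**3. Is it a slip in one sentence?** No. The Nutritional assessments section and the Statistical analysis plan section use the same three labels, and both stop at moderate.

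**4. Does another section supply a higher class?** No. The NRS-2002 has a single cut at 3. The only scale in the protocol with a severe grade is the HADS, whose bands are closed: 0–7 normal, 8–10 mild, 11–14 moderate, 15–21 severe.

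**5. Are patients with high scores kept out by eligibility?** Not on nutritional grounds. The exclusion criteria do not mention nutritional status. The limit on expected survival (less than 6 months) may remove some very ill patients, but it is not a malnutrition criterion.

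**6. How does the exposure enter the models?** The Statistical analysis plan section names logistic, linear, GEE and Cox models but does not say whether nutritional status enters them as a class or a score.

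**The case against.** The strongest reply is that this is a query about a label and that several larger claims do not follow from it. Most of that stands.

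- A reader might infer that the three classes are the fixed analysis grouping. The Statistical analysis plan section offers them only as an example, in the paragraph on descriptive comparisons.
- A reader might infer that the score is never used. That is not established. The planned Pearson or Spearman correlations with the psychosocial scales fit a numeric score at least as well as a three-level class, and the coding of an exposure is often left to a separate analysis plan, which is not at hand.
- A reader might infer that the study cannot show a gradient above 7 points. The mPG-SGA is scheduled at every visit, as are BMI, weight loss, arm circumference, skinfold and grip strength. Only the class is blind above 7.
- A reader might infer that severe cases are mixed in with moderate ones and that the risk of moderate malnutrition is overstated by some percentage. That presupposes a severe cut-off and hazard ratios that the documents do not contain. An estimate for 7 points or more is a valid estimate for that group.

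What the reply does not remove is the label. The protocol attributes the bands to a cited validation source, but whatever that source says, this document calls an unbounded worst class moderate and grades its primary exposure by severity. That is something stated, not a detail left open.

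**Conclusion.** The point holds in limited form. As written, every mPG-SGA score of 7 or more is classed as moderate malnutrition. A class-based result under that name would describe the whole band, and changes inside the band would not appear as changes of class. This follows from the text and needs no numerical assumption.

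The documents do not show whether a higher class was dropped, the top band was mislabelled, or the cited version has only three classes. They give neither the maximum score nor the share of patients well above 7, so the size of any effect on the results cannot be computed. Use of the score as the exposure is neither stated nor excluded. This is an inexpensive improvement in clarity and in use of the data, not a defect that invalidates the design.

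**What to change.** 1. Check the top band's label and cut-offs against the validated version that the protocol cites, then make the Nutritional assessments and Statistical analysis plan sections agree. No cut-off is proposed here, because the documents do not support one.
2. Until that is settled, report the group by its definition, mPG-SGA 7 points or more, and not as moderate. Describing the band by its score avoids guessing which label was intended.
3. State that the mPG-SGA total score will be analysed as a continuous exposure, linear with a spline check, alongside the classes in the Cox, logistic and GEE models. Where a GEE models nutritional status itself, the score would be the response. Differences and changes above 7 points are then retained whatever labels are adopted.

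Cost: wording in two sections and a small amount of extra analysis. No new data collection is needed, because the tool is already scheduled at every visit; the recorded score must be kept and not only the class.
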